6.2.2. Demographics

Descriptive statistics will be calculated for the following continuous demographic and baseline characteristics: age (weeks), weight (kg, z-score), length (cm, z-score) and weight-for-height z-score. Number and percentage of subjects will be provided for categorical variables such as gender, race, ethnicity, maternal COVID-19 infection history, maternal COVID-19 vaccine status, and maternal breastfeeding status. The summaries will be presented separately by vaccination group as defined in Section 6.1, based on the FAS, Randomization Set (Part 2), Per-Protocol (PP) Set, Per-Protocol Immunogenicity Subset (PPIS), PPIS-Neg, Safety Set, mITT Set, and mITT-1 Set.

Participants in Part 1 and Part 2 of the study who receive the same mRNA-1273.214 dose level may be combined. If the Safety Set differs from the Randomization Set in Part 2 (e.g., subjects randomized but not received any study injection; subjects received study vaccination other than the vaccination group they were randomized to), the analysis may also be conducted using the Randomization Set.

For screened failure subjects, age, as well as gender, race, ethnicity will be presented in a listing.

In addition, subjects with any inclusion and exclusion criteria violation will also be provided in a listing.

6.2.3. Medical History

Medical history data will be coded by system organ class (SOC) and preferred term (PT) using the Medical Dictionary for Regulatory Activities (MedDRA).

The number and percentage of participants with any medical history will be summarized by SOC and PT based on Safety Set. A participant will be counted only once for multiple events within each SOC and PT. SOC will be displayed in internationally agreed order. PT

will be displayed in descending order of frequency of the total mRNA-1273.214 group with all dose level combined in Part 1 and the mRNA-1273.214 group in Part 2 and then alphabetically within SOC.

Medical history data and maternal medical history will be presented in a listing.

6.2.4. Prior and Concomitant Medications

Prior and concomitant medications and non-study vaccination will be coded using the World Health Organization (WHO) drug dictionary (WHODD). The summary of concomitant medications will be based on the Safety Set. Categorization of prior, concomitant, and post medications is summarized in Table 4.

The number and percentage of subjects using concomitant medications and non-study vaccination during the 7-day follow-up period (i.e., on the day of injection and the 6 subsequent days) and during the 28-day follow-up period after each injection (i.e., on the day of injection and the 27 subsequent days) will be summarized by vaccination groups as defined in Section 6.1 as follows:

- Any concomitant medications and non-study vaccination within 7 Days Post Injection
- Any concomitant medications and non-study vaccination within 28 Days Post Injection
- Antipyretic or analgesic medication within 28 Days Post Injection

A summary table of non-study vaccination that continued or newly received at or after the first injection through 28 days after the last injection will be provided by PT in descending frequency in the mRNA-1273.214 Total group with both dose levels combined for Part 1 and the mRNA-1273.214 group for Part 2.

A summary table of concomitant medications that continued or newly received at or after the first injection through 28 days after the last injection will be provided by PT in descending frequency of mRNA-1273.214 Total group with both dose levels combined for Part 1 and the mRNA-1273.214 group for Part 2.

Prior, concomitant and post medications and non-study vaccination, and maternal prior/concomitant medications and vaccination will be presented in a listing.

Concomitant Procedures will be presented in a listing.

6.2.5. Study Exposure

Study IP administration data will be presented in a listing.

Study duration will be summarized by the following: since randomization, since the first injection, and since the second injection.

- Study duration from first injection (days) = earliest date of (study discontinuation, study completion, death, and data cutoff date) date of first injection +1.
- Study duration from second injection (days) = earliest date of (study discontinuation, study completion, death, and data cutoff date) date of second injection +1.

6.2.6. Major Protocol Deviations

Major protocol deviations are a subset of protocol deviations that may significantly impact the completeness, accuracy, or reliability of the study data or that may significantly affect a subject's rights, safety, or well-being. Major protocol deviations rules will be identified, reviewed and finalized before database lock in accordance with the protocol deviation rule document.

The number and percentage of the subjects with each major protocol deviation type will be by vaccination group as defined in Section 6.1 based on the Full Analysis Set for Part 1 and will be provided by vaccination group based on the Randomization Set for Part 2.

Major protocol deviations will be presented in a listing.

6.2.7. COVID-19 Impact

A listing will be provided for COVID-19 impact.

6.3. Safety Analysis

Safety and reactogenicity will be assessed by clinical review of all relevant parameters including solicited ARs (local and systemic), unsolicited AEs, SAEs, MAAEs, AESIs, AEs leading to withdrawal from study vaccine and/or study participation, and physical examination findings. Solicited ARs and unsolicited AEs will be coded by SOC and PT according to the MedDRA. A modified version of The Toxicity Grading Scale for Healthy Adult and Adolescent Volunteers Enrolled in Preventative Vaccine Clinical Trials (DHHS 2007) is used in this study for solicited ARs as presented in Table 7 in Section 8.11.3 of the protocol.

All safety analyses will be based on the Safety Set, except summaries of solicited ARs which will be based on the Solicited Safety Set. All safety analyses will be provided by study part and vaccination group unless otherwise specified.

Subgroup analysis may be done for the following subgroups:

- Sex (male, female)
- SARS-CoV-2 status at baseline
- Maternal COVID-19 vaccine status
- Maternal COVID-19 infection status
- Race
- Ethnicity

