4.2. Scientific Rationale for Study Design

This Phase 2 study is designed as a two-part, dose-finding and open-label (Part 1), and randomized, observer-blinded, and placebo-controlled study (Part 2) to demonstrate the

Protocol: mRNA-1273-P206, Original

immunogenicity and safety of the mRNA-1273.214 vaccine in participants aged 12 weeks to < 6 months. This pediatric study is intended to confirm safety in infants between 12 weeks to < 6 months of age and bridge immunogenicity between infants and adults (> 18 years of age) enrolled in the pivotal adult Phase 3 study (Study mRNA-1273-P301). It is necessary to demonstrate noninferiority of the induced immune response in infants compared with that in adults to infer vaccine effectiveness in this age group.

Part 1 of the study is designed to dose escalate starting with a low dose level in Arm 1. Arm 2 will test the next higher dose level if there are no safety concerns (after IST review of 25 participants in Arm 1 who have reached Day 64). Safety and immunogenicity analysis after both Arm 1 and Arm 2 have completed enrollment and participants have reached Day 85 will determine the dose level for Part 2. Part 2 of the study is designed to assess safety and immunogenicity of the selected dose level from Part 1 in a randomized, placebo-controlled design. This randomization and placebo arm is necessary to assess safety since no trials have assessed an mRNA vaccine in this age group.

With SARS-CoV-2 expected to be circulating in the general population during the study, all participants will provide pre- and post-injection blood samples for analysis of antibodies to non-vaccine antigens as described in the SoA (Table 1). In addition, participants will have nasal swab samples collected before vaccination according to the SoA. Furthermore, in case of any signs or symptoms or MAAEs suggesting SARS-CoV-2 infection in a participant, an additional nasal swab sample will be collected to confirm the diagnosis of SARS-CoV-2 via RT-PCR. Additionally, clinical information will be carefully collected to evaluate the severity of the clinical case.

Since it is possible that participants are naturally exposed to SARS-CoV-2 through community exposure, the nasal swab samples collected before study injection and the serologic assays performed for Ab responses to non-vaccine antigen(s), may help to discriminate between natural infection and vaccine-induced Ab responses, should such discrimination be needed.

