9.5.3. Exploratory Analyses

The exploratory analyses of the effectiveness of mRNA-1273.214 will evaluate the incidence of COVID-19, SARS-CoV-2 infection regardless of symptomatology or severity, severe COVID-19, etc.

To evaluate the incidence of COVID-19 after vaccination with mRNA-1273.214 or placebo, the incidence rate will be provided by vaccination group, calculated as the number of cases divided by the total person-time.

For serologically confirmed SARS-CoV-2 infection or COVID-19, regardless of symptomatology or severity, infection rate will be provided by vaccination group. The same analysis will be performed for asymptomatic SARS-CoV-2 infection.

Protocol: mRNA-1273-P206, Original

The exploratory analyses of the effectiveness will be performed primarily on the PP Set, unless specified otherwise. Sensitivity analyses for effectiveness will be performed on other select analysis sets, eg, mITT and/or mITT-1.

For the exploratory analyses for mRNA-1273.214 against other variants of interests, the same analyses methods described in Section 9.5.1 will be employed to analyze immunogenicity data. More details of exploratory analyses will be described in the SAP before database lock.

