4.3. Sample Size and Power

In Part 2, approximately 600 infant participants 12 weeks to < 6 months of age will be enrolled at the dose level selected for Part 2, with an mRNA-1273.214 to placebo ratio of 1:1. Assuming 10% to 15% participants are not negative SARS-CoV-2 status at baseline, it is estimated that there will be a minimum of approximately 250 evaluable participants in the mRNA-1273.214 arm eligible for immunogenicity analyses.

The sample size of approximately 300 infant participants in the mRNA-1273.214 arm in Part 2 is considered to be sufficient to support a safety assessment. There is at least 90% probability to observe at least 1 participant with an AE at a true AE rate of 1% in this group.

The sample size calculation for each of the 2 primary noninferiority hypothesis tests (H_A^1 and H_A^2) was performed, and the larger sample size was chosen for the study.

• With approximately 250 evaluable participants receiving mRNA-1273.214 in the Per-Protocol Immunogenicity Subset - Negative (PPIS-Neg) in Study mRNA-1273-P206 and adults (≥ 18 years of age) in Study mRNA-1273-P301, there will be at least 90% power to demonstrate noninferiority of the immune response against Omicron variant, as measured by the geometric mean concentration (GMC) or GM level, in infant population at a 2-sided alpha of 0.05, compared with that in adults (≥ 18 years of age) in Study mRNA-1273-P301 receiving mRNA-1273, assuming an underlying geometric mean ratio (GMR) (which is calculated as ratio of GMC or

- GM level) value of 1 and the standard deviation of the natural log-transformed concentration/level is assumed to be 1.0, and a noninferiority margin of > 0.667.
- With approximately 250 evaluable participants receiving mRNA-1273.214 in the PPIS-Neg in Study mRNA-1273-P206 and adults (≥ 18 years of age) in Study mRNA-1273-P301, there will be at least 90% power to demonstrate noninferiority of the immune response against Omicron variant as measured by SRR in infants at a 2-sided alpha of 0.05, compared with SRR against Omicron variant in adults ≥ 18 years of age in Study mRNA-1273-P301 receiving mRNA-1273, assuming SRR of 60% to 70% in Study mRNA-1273-P301, true SRR improvement of 10% in infants from Study mRNA-1273-P206 compared with adults from Study mRNA-1273-P301, and a noninferiority margin of 5%.

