4.4. Randomization

Random assignment of participants in Part 2 of the study will use a centralized interactive response technology (IRT), in accordance with pre-generated randomization schedules. Approximately 600 participants will be randomized in a 1:1 ratio to the mRNA-1273.214 arm or placebo arm (n = approximately 300 participants in each group).

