be summarized by vaccination group, toxicity grade, days of reporting and injection. In addition, a bar plot will be created to display the percentage of participants who reported each individual solicited AR after each injection.

A two-sided 95% exact confidence interval (CI) using the Clopper-Pearson method will be provided for the percentage of subjects who reported any solicited local AR, solicited systemic AR, or any solicited AR.

The onset of individual solicited AR is defined as the time point after each injection at which the respective solicited AR first occurred. The number and percentage of subjects with onset of individual solicited AR will be summarized by vaccination group, study day relative to the corresponding injection (Day 1 through Day 7), and injection.

The duration will be calculated as the end date/day of the solicited AR event – start date/day of the solicited AR event + 1, regardless of whether it is intermittent or continued. If the solicited AR continues beyond 7 days, the days a solicited AR is reported after 7 days will be included (e.g., an event that lasted 5 days in the first 7 days post injection and 3 days beyond 7 days post injection, the duration will be reported as 8 [5+3] days).

Characteristics of solicited ARs during the 7-day follow-up period after each injection will be provided, including descriptive statistics of day of onset and duration in days, as well as number and percentage of solicited ARs persisting beyond 7 days.

Solicited ARs collected on eDiary and those collected on reactogenicity aCRF will be provided in a listing, and the maximum grade from eDiary and aCRF will be presented. All solicited ARs that continue beyond 7 days post injection will be presented in separate data listings.

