6.5.2. Analysis Method

The number and percentage of subjects who had an event (i.e., COVID-19 case) will be summarized for the PP set, and FAS.

The incidence rate will be calculated as the number of cases divided by the total persontime (person-year or person-month). The 95% CI of the incidence rate will be calculated using the exact method (Poisson distribution) and adjusted by person-time.

Person-time is defined as the total time from randomization date in Part 2 to the date of event, last date of study participation, censoring time, or efficacy data cutoff date, whichever is earlier.

Descriptive summaries of clinical profile and immunologic endpoints to characterize participants with COVID-19 or SARS-CoV-2 infection during the study will also be provided.

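### Part 2 randomises infants to placebo in order to assess safety, but plans no vaccine-versus-placebo estimate with a confidence interval

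*SAP*

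**What the plan says.** On the design, SAP 4.4 states: "Approximately 600 participants will be randomized in a 1:1 ratio to the mRNA-1273.214 arm or placebo arm". Protocol 4.2 gives the reason for the control arm: "This randomization and placebo arm is necessary to assess safety since no trials have assessed an mRNA vaccine in this age group". Safety and reactogenicity are a primary objective of Part 2 (Protocol Table 3, SAP 2.1).

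On the analysis, SAP 6.3 states "Safety and reactogenicity will be assessed by clinical review of all relevant parameters" and "All safety analyses will be provided by study part and vaccination group unless otherwise specified". For solicited reactions, SAP 6.3.2 adds: "A two-sided 95% exact confidence interval (CI) using the Clopper-Pearson method will be provided for the percentage of subjects" reporting any local, any systemic or any solicited reaction. Protocol Table 9 plans a confidence interval for solicited reactions only. Its interval column is empty for unsolicited AEs, SAEs, MAAEs, severe AEs and AESIs.

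For the exploratory COVID-19 and infection endpoints, SAP 6.5.2 gives incidence rates: "The 95% CI of the incidence rate will be calculated using the exact method (Poisson distribution) and adjusted by person-time". Protocol 9.5.3 presents these rates by vaccination group and names among its topics "SARS-CoV-2 infection regardless of symptomatology or severity, severe COVID-19, etc". SAP 6.5 lists three incidence endpoints, and severe COVID-19 is not one of them.

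The formal between-group contrasts in the plan are the geometric mean ratio and the seroresponse difference, both against adults in Study P301. All ten Part 2 hypotheses in SAP 4.2 are of that kind.

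**The concern.** An arm included to assess safety does its work through the comparison with the vaccine arm. The plan reports each arm separately and stops there. A reader of the study report could subtract the percentages, but would have no planned interval saying how far the difference could be due to chance.

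Solicited reactions show the need most clearly. Protocol 8.11.3 and SAP 6.3.2 class all of them as related to the injection, and the list includes irritability or crying, sleepiness, loss of appetite and fever. Infants show these without vaccination too, so the causality label cannot separate background from vaccine effect. Vaccine minus placebo can.

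The sponsor already reads its earlier trials by contrast with placebo. Protocol 2.3.2 picks out P301 events at a rate at least 1.5 times placebo, and P204 events exceeding placebo by more than 1 percentage point. If Part 2 is read the same way with no interval, a 1-point excess cannot be told from noise.

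**Working it through.** **Inputs.** About 300 infants per arm (SAP 4.4). P204 rates for ages 6 months to < 2 years (Protocol 2.3.2). A two-sided 95% level, which the documents set for immunogenicity only and which is assumed here for a safety contrast. Other rates below are illustrative and are marked so.

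**1. The plan's own safety figure.** SAP 4.3 states "There is at least 90% probability to observe at least 1 participant with an AE at a true AE rate of 1" per cent. Check: 1 − 0.99^300 = 1 − 0.049 = 95.1%. The statement holds. It concerns the vaccine arm alone and says nothing about the comparison with placebo.

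**2. Precision of the estimate that is not planned.** With a common rate p and 300 per arm, the half-width of the 95% interval for the risk difference is about 1.96 × √(2p(1 − p)/300).

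| p | Half-width (percentage points) |
|---|---|
| 1% | 1.6 |
| 10% | 4.8 |
| 48.2% | 8.0 |

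Set against this, the P204 excess in any unsolicited AE was 49.3 − 48.2 = 1.1 points, and in injection site lymphadenopathy 1.4 − 0.2 = 1.2 points. Differences of that size need an interval beside them to be interpreted.

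**3. Per-arm intervals are a poor substitute.** Suppose, for illustration, that 60/300 (20%) on placebo and 90/300 (30%) on vaccine report a reaction. The Clopper-Pearson intervals are 15.6% to 25.0% and 24.9% to 35.5%, which just overlap. The difference is 10.0 points. Its simple half-width is 1.96 × √(0.2 × 0.8/300 + 0.3 × 0.7/300) = 6.9 points, and the Miettinen-Nurminen interval is 3.1 to 16.9 points, which excludes zero.

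**4. What an overlap reading would cost, if someone used it.** The plan contains no such rule, so this is an illustration only. Exact enumeration over all binomial outcomes at 300 per arm gives the probability of showing a difference:

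| True rates (assumed) | Score test of the difference | Non-overlap of Clopper-Pearson intervals |
|---|---|---|
| 20% v 30% | 81% | 49% |
| 10% v 18% | 81% | 48% |
| 1% v 4% | 69% | 26% |
| 20% v 35% | 99% | 90% |
| 10% v 30% | about 100% | about 100% |

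The normal approximation with equal standard errors is Φ(z_power + 1.96 − 1.96√2). At 80% power this is Φ(0.842 + 1.960 − 2.772) = Φ(0.030) = 51.2%. At 90% it is 68.1%, and at 99% it is 93.5%. The cost depends on the true effect and shrinks as the effect grows.

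**5. Incidence endpoints.** Take 25 v 45 cases on equal person-time (illustrative). The exact Poisson intervals for the counts are 16 to 37 and 33 to 60, which overlap. The rate ratio is 25/45 = 0.56. Given 70 cases in all, the exact binomial interval for the vaccine share, 25/70, is 0.246 to 0.481. The transformation p/(1 − p) turns this into a rate-ratio interval of 0.33 to 0.93.

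**6. Severe COVID-19.** Protocol 9.5.3 says it will be evaluated. SAP 6.5 does not list it, and SAP 7 records no change. Protocol Table 3, however, has no endpoint for the incidence of severe COVID-19. It has only a description of clinical severity, which SAP 3.3 repeats and SAP 6.5.2 covers in its clinical-profile summaries. The mismatch is real but narrow.

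**The case against.** Descriptive safety reporting is a declared and consistent choice. The objective is to evaluate safety, the sizing statement is single-arm, no safety hypothesis exists, and the stated method is clinical review. The DSMB sees unblinded data, and its outputs are defined in a charter not available here. COVID-19 incidence is exploratory. All of this stands. It makes the gap an omission and not an error of calculation. But DSMB review during the trial does not supply the estimate for the study report.

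Two stronger readings are tempting, and the documents support neither.

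- A reader might infer that the plan loses about 30 points of power for safety. Power needs a test or decision rule, and the plan has none for safety. Nothing tells anyone to judge by overlap of intervals, and for unsolicited AEs, SAEs, MAAEs and AESIs no intervals are planned that could overlap. The cost of that hypothetical rule also runs from almost nothing (10% v 30%) to 43 points (1% v 4%).
- A reader might infer that the randomised comparison goes unreported. Per-arm percentages and incidence rates are planned, so the point difference and ratio follow from the tables. Only the interval is missing.

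Three further limits are fair. An interval would not rescue detection of small effects: at the P204 rates, a direct test with 300 per arm has about 6% power for any unsolicited AE and 38% for injection site lymphadenopathy. The Safety Set is analysed as treated, so a safety contrast in it is not strictly by randomisation. And SAP 7 records an enrolment pause during Part 1 Arm 2; the Part 2 text still stands, but the figures here assume Part 2 is run at full size.

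**Conclusion.** The point holds as a missing estimate. Neither document specifies a vaccine-versus-placebo difference, ratio or interval for any safety or incidence endpoint, although the protocol calls the placebo arm necessary for assessing safety. The excess over placebo would be reported without a measure of its uncertainty. With 300 per arm and the assumed 95% level, that uncertainty is about ±1.6 points at a 1% rate and ±8.0 points at 48.2%.

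The consequence is greatest for solicited reactions, where relatedness is assigned by rule. As an illustration only, a reader who judged solicited reactions by overlap of the two intervals would turn a contrast with about 80% power into one with about 48% (20% v 30%), and would lose less for larger effects.

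No planned conclusion is invalidated. The change is a cheap improvement, worth making before Part 2 data are unblinded.

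**What to change.** - **SAP 6.3, Part 2:** add the vaccine-minus-placebo risk difference with a 95% Miettinen-Nurminen interval for any and for Grade 3 or higher solicited reactions after each injection, and for unsolicited AEs, MAAEs, SAEs and AESIs. Keep the existing safety sets and state that the contrast is as treated.
- **SAP 6.5.2:** add the vaccine-to-placebo incidence-rate ratio with an exact conditional 95% interval for COVID-19 and for SARS-CoV-2 infection.
- **SAP 6.5:** tabulate severe COVID-19 by arm to match Protocol 9.5.3.
- **Labelling:** state that these are descriptive estimates with no multiplicity-controlled claims.

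The cost is SAP wording and some programming. The Miettinen-Nurminen method is already used in SAP 6.4.3, and the rate ratio uses counts and person-time already planned. Nothing changes in conduct, dose or sample size. The downside is that, with many endpoints, some difference intervals will exclude zero (or ratio intervals exclude one) by chance, which is why the descriptive label is needed.
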